8.2.2. Safety Analyses

All summaries will use the safety analysis set.

Adverse events which will be graded according to grades of severity specified in the Common Technology Criteria for Adverse Events Version 3.0 (CTCAE v3.0). Pfizer data standards (PDS) will be used to summarize all safety data.

Patient baseline characteristics (demography, breast cancer history, medical history, primary diagnosis, lab data, treatment history related to primary diagnosis, history of hormonal therapy received before Aromasin, location of primary diagnosis, histopathological classification and grade, TNM stage) will also be summarized according to PDS. Vital signs, ECOG status, laboratory data and physical examination will be summarized by visit using observed data as well as each patient's last available value.

[REDACTED]

9. REFERENCES

2. Hall, W. J. and Wellner, J. A. (1980), "Confidence Bands for a Survival Curve for Censored Data," *Biometrika* 69.

The following types of cancer recurrence will be derived from the Cancer Event Assessment CRF:

- Local: "Recurrent Disease" is checked on the CRF and "Disease Site" is marked "Breast".
- Distant: "Recurrent Disease" is checked on the CRF and "Disease Site" is marked something other than breast (brain, lung, bone, lymph node, liver, other).
- Time to Locoregional recurrence: Time from inclusion into the study to the date of the first documentation of locoregional recurrence. Specifically, time to Locoregional recurrence is (date of inclusion into the study) – (first date of documented locoregional recurrence) +1.

Locoregional recurrence is defined as any recurrence in the ipsilateral breast, chest wall or axillary lymph nodes.

- If HER2 FISH, HER2 CISH and HER2 mutation are all undone or unknown, then
 - If HER2 IHC status = 3+, HER2 is positive.
 - If HER2 IHC status = 0 or 1+, HER2 is negative.
 - If HER2 IHC status = 2+ or unknown or undone, HER2 is unknown.

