6. STUDY PROCEDURES

6.1. Screening (within 2 years prior to Day 1)

Due to the non-interventional- study design at the time subjects were enrolled, the Informed consent form (ICD) permitted the collection of data related to screening procedures up to 2 years prior to Informed Consent being given. After the transition from a non-interventional study to an interventional, pragmatic study, the ongoing subjects must re-sign the ICD.

The following screening procedures (to the extent that they are available) must be performed prior to the start of treatment on study unless otherwise stated.

Patient signature on current Institutional Review Board (IRB)/Independent Ethics Committee (IEC) approved informed consent document.

Demographic data;

- Subject date of birth, gender, race.

Physical examination including examination of major body systems (General, Lungs, Heart, Musculoskeletal, Genitourinary, Neurological, Lymph nodes, Skin, Abdomen and Other), Easter Cooperative Oncology Group (ECOG) performance status, body weight, height (screening only), and vital signs (temperature, blood pressure, heart rate, respiratory rate).

Breast cancer history:

- Date of initial diagnosis of breast cancer;
- Tumor location: Left/right breast.

Performance status at diagnosis (Easter Cooperative Oncology Group Performance Status).

Histopathological diagnosis:

- Tumor, Lymph Node and Metastasis (TNM) current stage (as per AJCC, 2002);
- Hormone receptor status (ER/PR status);
- HER-2 receptor status (as per Breast Cancer National Comprehensive Cancer Network (NCCN) clinical practice guideline Chinese version v.1.2009).

Medical history:

- Concomitant illnesses;
- Concomitant drug and non-drug treatment (within 21 days prior to the start of treatment on study) including supportive therapy (calcium, bisphosphonates, etc).

Treatment history related to primary diagnosis:

- Surgery related to primary diagnosis:
 - Date of surgery;
 - Type of surgery;
 - Outcome of surgery.

- Chemotherapy (CT):
 - Adjuvant CT: Agent name, date of starting, stop date, number of cycles.
- Radiotherapy:
 - Site of radiotherapy;
 - Dates started and stopped;
 - Total dose.
- History of hormonal therapy received before Aromasin®:
 - Agent used;
 - Dosage and duration.

Baseline investigations (the updated investigation result prior to the start of the treatment on study)

- Hematology: hemoglobin, platelet count, white blood cell count, and differential count (percent);

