6.3.2. Final Visit

For each subject, the final visits will occur at completion the study drug or at the occurrence of any of the events signifying treatment termination (refer [Section 7.2](#)).

Observational Parameters collected at the Final Visit are identical to the Study Period Visits; with the addition of recurrence time and location, if the subject has recurrence.

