7.1. Efficacy Endpoint

The first occurrence of any of the following events constitutes an efficacy endpoint for the subject:

- Loco-regional/distant recurrence of the primary breast cancer;
- Appearance of a second primary or contralateral breast cancer;
- Death due to any cause.

Loco-regional recurrence is defined as any recurrence in the ipsilateral breast, chest wall or axillary lymph nodes.

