6.2. SECONDARY EFFICACY Endpoints

Locoregional/distant recurrence, appearance of 2nd primary or contralateral breast cancer, and death will also be summarized as follows:

- Time to each event.
- The proportion of subjects experiencing each event.
- The incidence rate (per annum) is defined as a ratio of the number of events and the total exposure time (in years) to Aromasin[®] therapy.

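### The SAP derivation text codes lymph-node recurrence as Distant, against its own definition of locoregional, and subtracts the dates in the wrong order for time to locoregional recurrence

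*SAP*

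**What the plan says.** The SAP text that derives recurrence types from the Cancer Event Assessment form stands after Section 9 (References) and before Appendix 2. It gives two site rules. A recurrence is Local if the disease site is Breast, and Distant if the site "is marked something other than breast (brain, lung, bone, lymph node, liver, other").

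The same text then states: "Locoregional recurrence is defined as any recurrence in the ipsilateral breast, chest wall or axillary lymph nodes". SAP 6.1 and Protocol 2.2.1 give the same definition, as does Protocol 7.1: "Loco-regional recurrence is defined as any recurrence in the ipsilateral breast, chest wall or axillary lymph nodes".

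For the timing, the text first describes the interval in words: "Time from inclusion into the study to the date of the first documentation of locoregional recurrence". It then gives a formula, introduced as the specific form of that description: ("date of inclusion into the study) – (first date of documented locoregional recurrence) +1".

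On reporting, SAP 6.2 says: "Locoregional/distant recurrence, appearance of 2nd primary or contralateral breast cancer, and death will also be summarized as follows". The list that follows covers time to each event, the proportion of subjects and the annual incidence rate.

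On data collection, Protocol 6.3.2 has the final visit repeat the study-period data "with the addition of recurrence time and location, if the subject has recurrence". Protocol 6.1 records "Tumor location: Left/right breast" at screening.

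**The concern.** Two instructions in the derivation text cannot be followed without contradicting the plan's own definitions.

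First, an axillary-node recurrence is Distant under the site rule and locoregional under the definition a few lines later. Nothing visible separates axillary from other nodes.

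Second, the subtraction runs backwards, so a program that follows it produces zero or negative times for every recurrence after the day of inclusion. Those are not usable survival times.

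At stake are the local/distant split and time to locoregional recurrence. The study is descriptive and has no hypothesis test, so correct classification and timing of events is much of what it delivers.

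**Working it through.** There is no sample-size or power figure to reproduce, because the plan made no such estimate. The check applies the printed rules and compares the results with the plan's own definitions.

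**Site rule.** Each disease site named in the rule was coded as printed and set against the definition in SAP 6.1 and Protocol 7.1.

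| Site on form | Printed rule | Plan's definition |
|---|---|---|
| Breast | Local | Locoregional if ipsilateral |
| Brain, lung, bone, liver | Distant | Not locoregional |
| Lymph node | Distant | Locoregional if axillary |
| Other | Distant | Locoregional if it holds chest wall |

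The lymph-node row is a direct conflict, since the rule names that site. Two rows raise further questions that depend on the form, which is not shown: whether chest wall is entered under other, and whether contralateral disease could be entered as a breast recurrence and so coded Local. These are points to check, not shown errors.

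**Date formula.** Let d be the days from inclusion to first documented locoregional recurrence.

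- Printed: inclusion − recurrence + 1 = 1 − d
- Following the verbal description: recurrence − inclusion + 1 = d + 1
- Difference: (d + 1) − (1 − d) = 2d

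| d (days) | Printed | Intended |
|---|---|---|
| 0 | 1 | 1 |
| 1 | 0 | 2 |
| 2 | −1 | 3 |
| 182 (time point in the sample code, SAP Appendix 2.2) | −181 | 183 |
| 365 | −364 | 366 |
| 730 | −729 | 731 |
| 1095 | −1094 | 1096 |

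The two agree only at d = 0.

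**Size of the site-rule effect.** The inputs are 550 patients (SAP 2.1) and 2 to 3 years of treatment (Protocol 3). If all 550 complete treatment, exposure is 550 × 2 = 1,100 to 550 × 3 = 1,650 person-years; shorter exposure makes the rate shifts larger. One moved event is 1/550 = 0.18 percentage points, and 1/1,650 to 1/1,100 = 0.06 to 0.09 events per 100 person-years. The numbers of axillary recurrences below are assumptions.

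| Assumed events moved | Shift in proportion (percentage points) | Shift in rate per 100 person-years |
|---|---|---|
| 1 | 0.18 | 0.06 to 0.09 |
| 5 | 0.91 | 0.30 to 0.45 |
| 10 | 1.82 | 0.61 to 0.91 |

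These shifts appear only where locoregional and distant recurrence are tabulated separately.

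**The case against.** The strongest reply is that Local is not the same term as locoregional. Time to locoregional recurrence has its own bullet and a correct definition, so a careful programmer could use that definition and ignore the Local/Distant labels. This stands in part: the site rule is not shown to corrupt the time variable on every reading. But an axillary recurrence would still be labelled Distant against the protocol, and no visible rule would then derive locoregional status from the form.

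The derivation text is also visibly incomplete in the copy reviewed: its heading and the opening HER2 lines are absent. A rule for regional disease may have been lost. That limits what can be said about absent rules, but it does not remove the printed line that names lymph node as Distant.

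The reversed subtraction is plainly a drafting slip. The sentence before it has the right direction, as does SAP 8.2.1 for the primary endpoint, and negative times would probably be noticed. That lowers the chance of harm, but the formula should still be corrected.

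Finally, SAP 6.2 and 8.2.1 list locoregional and distant recurrence as one item. If they are only ever pooled, the site coding changes no summary of that item. This stands, and it limits the size of the problem.

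**Conclusion.** The concern holds on both counts. Followed as printed, the SAP labels axillary-node recurrence Distant against its own definition, and gives times to locoregional recurrence that are wrong by 2d days and zero or negative from day 1 onward.

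The reach is limited. The site coding does not alter the composite primary endpoint, in which both recurrence types are events, and the reversed formula is printed only for time to locoregional recurrence. No time to distant recurrence is visible. The effect on the split is 0.18 percentage points per misplaced event, given 550 patients and separate reporting; the actual number of such events cannot be known from the documents. This should be fixed before the final analysis is programmed. Confidence is high that the two printed errors exist; their effect on the reported results depends on what is tabulated.

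**What to change.** 1. Derive locoregional recurrence as the plan defines it (ipsilateral breast, chest wall, axillary node), using the recurrence location from the final visit and the tumour side from screening. Code other sites of recurrence as distant, and assign contralateral breast disease to the second-primary/contralateral event.
2. Query nodal and other sites whose location is unclear, and state how cases that stay unresolved are shown.
3. Write the time as first documented locoregional recurrence date − inclusion date + 1.
4. State in SAP 6.2 whether locoregional and distant recurrence are summarised separately, pooled, or both.

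The cost is SAP wording, some derivation programming and a number of data queries that the documents do not let one estimate. No new patients or visits are needed. Protocol 6.3.2 does not say whether the recorded location distinguishes axillary from other nodes, so some cases may remain unclassified.

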9.3.1. Analysis of Primary Endpoint

The primary efficacy variable will be time-to-event, where event is defined as the earliest occurrence any of the following:

- Loco-regional/distant recurrence of the primary breast cancer;
- Appearance of a second primary or contralateral breast cancer;
- Death due to any cause.

Time-to-event will be calculated as the time from date of enrollment to first objective documentation of the event defined above. In the analysis of time to event, subjects lost to follow-up and subjects who are still being followed at the time of analysis with no documented event will be censored at the last date the subject was known to be event-free.

The Kaplan Meier non-parametric estimate will be used to summarize the survival distribution and median for time-to-event. Ninety-five percent confidence intervals for the survival distribution will be computed.

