9.3.2. Analysis of Secondary Endpoints

Loco-regional/distant recurrence, appearance of a second primary or contralateral breast cancer, and death will also be summarized as follows:

- Time to each event;
- The proportion of subjects experiencing the event;
- The incidence rate (per annum) is defined as a ratio of the number of events and the total exposure time (in years) to Aromasin® therapy;
- The relationship between Her2 overexpression level and time-to-event.

Categorical data will be presented using counts, percentages and 95% confidence intervals for percentages. Continuous data will be reported using n, mean, standard deviation, median and range, 95% confidence interval may also be presented where specified. The Kaplan Meier non-parametric estimate will be used to summarize the survival distribution and median for time-to-event, 95% confidence intervals for the survival distribution will be computed.

CCI

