4. HYPOTHESES AND DECISION RULES

4.1. Statistical Hypotheses

This study is non-comparative and no inferential statistical analyses are planned. Analyses will consist of descriptive statistics and corresponding 95% 2-sided confidence intervals when appropriate.

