8.2. Statistical Analyses

8.2.1. Efficacy Analyses

All summaries of efficacy parameters will be reported within the FAS population. Analyses will be primarily descriptive in nature, and therefore no statistical sample size estimation was performed.

Primary analysis

The primary analysis is time-to-recurrence, where recurrence is defined as the earliest occurrence any of the following:

- Locoregional/distant recurrence of the primary breast cancer.
- Appearance of 2nd primary or contralateral breast cancer.
- Death due to any cause.

Time-to-recurrence is calculated as the time from date of enrollment to first objective documentation of the recurrence defined above. In the analysis of time to recurrence, subjects lost to follow-up and subjects who are still being followed at the time of analysis with no documented event will be censored at the last date the subject was known to be event-free. The Kaplan Meier non-parametric estimate will be used to summarize the survival distribution and median for time-to-event. 95% confidence interval for median time to event (method of Brookmeyer and Crowley 1982) and 95% confidence bands for the survival distribution (method of Hall and Wellner, 1980) will be computed.

Secondary analyses

Locoregional/distant recurrence, appearance of 2nd primary or contralateral breast cancer, and death will also be summarized as follows:

- Time to each event will be summarized similarly as the primary analyses for time-to-recurrence (See [Section 8.1.3](#)).
- Summary statistics for the proportion of subjects experiencing each event.
- Summary statistics for the incidence rate (per annum), defined as a ratio of the number of events and the total exposure time (in years) to Aromasin[®] therapy.

CCI [REDACTED]

[REDACTED]

[REDACTED]

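### Minor, wrong as written: the SAP formula for time to locoregional recurrence subtracts the dates in reverse order, giving zero or negative times for any recurrence after the day of inclusion

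*SAP*

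**What the plan says.** The derivation text printed after SAP section 9 (References) defines the variable twice, in adjacent sentences.

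- In words: "Time from inclusion into the study to the date of the first documentation of locoregional recurrence".
- As a calculation, introduced as the specific form of that definition: "date of inclusion into the study) – (first date of documented locoregional recurrence) +1".

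Elsewhere both documents run time forward. SAP 8.2.1 says of the primary analysis: "Time-to-recurrence is calculated as the time from date of enrollment to first objective documentation of the recurrence defined above". Protocol 9.3.1 says: "Time-to-event will be calculated as the time from date of enrollment to first objective documentation of the event defined above".

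The place where a component time would be used is the secondary analysis. SAP 8.2.1 says: "Time to each event will be summarized similarly as the primary analyses for time-to-recurrence". SAP 6.2 introduces the list of components with "Locoregional/distant recurrence, appearance of 2nd primary or contralateral breast cancer, and death will also be summarized as follows", and Protocol 9.3.2 has nearly the same sentence. Both treat locoregional and distant recurrence as one item.

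**The concern.** The second sentence is meant to make the first exact, but it reverses its direction. Inclusion comes before recurrence, so inclusion date minus recurrence date is negative for every recurrence after the day of inclusion. Adding 1 does not repair that beyond the first day.

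This is current SAP text, not the revision history. Both date labels, the minus sign and the +1 are intact, so the reversal is not an effect of PDF extraction or redaction. Nothing readable in either document corrects it.

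It matters because this is derivation text, which a programmer codes from. It is the only explicit date formula for an event time in the readable SAP, and the SAP gives no rule for zero or negative times. A programmer must either code impossible values or depart from the SAP without authority to do so. What is at stake is any secondary time-to-event summary built on this variable.

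**Working it through.** **Inputs**

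- Printed rule: inclusion date − recurrence date + 1 (SAP, derivation text after section 9).
- Described direction: inclusion to first documented locoregional recurrence (same place, preceding sentence), consistent with SAP 8.2.1 and Protocol 9.3.1.
- Days per month for plots: 365.25/12 = 30.4375 (SAP 8.1.3).
- Visit interval, for illustration only: about 6 months (Protocol 6.3.1), so 6 × 30.4375 = 182.625, rounded to 183 days.
- Assumption: the +1 in the printed formula is intended. The prose does not state it.

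**Algebra**

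Let I be the inclusion date and R = I + g the date of first documented locoregional recurrence, with g ≥ 0. Protocol 4.2 excludes women with relapse evident before Aromasin, so g ≥ 0 is the ordinary case.

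- Printed: I − R + 1 = 1 − g.
- Described, keeping the +1: R − I + 1 = g + 1.
- Difference: (g + 1) − (1 − g) = 2g days.

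**Numbers**

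| g (days) | Printed (days) | Described (days) | Difference (days) |
|---|---|---|---|
| 0 | 1 | 1 | 0 |
| 1 | 0 | 2 | 2 |
| 2 | −1 | 3 | 4 |
| 183 | −182 | 184 | 366 |
| 365 | −364 | 366 | 730 |
| 730 | −729 | 731 | 1460 |

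In months at g = 183: −182/30.4375 = −5.98 printed, against 184/30.4375 = 6.05 described.

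The two rules agree only at g = 0. The printed result is zero at g = 1 and negative from g = 2.

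**Sensitivity to the +1**

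If the intended interval were g rather than g + 1, the difference would be g − (1 − g) = 2g − 1 days, or 365 instead of 366 at g = 183. The reversal remains under either convention.

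**The case against.** The strongest reply is that this is a slip of the pen with no ambiguity of intent. The sentence just before the formula gives the direction, and the primary analysis text in both documents agrees. That is true. It explains why the correction needs no judgement, but it does not make the formula right.

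Second, no planned analysis is shown to depend on this variable alone. The secondary endpoint lists treat locoregional and distant recurrence together, so a separate Kaplan-Meier analysis of locoregional recurrence is an inference, although the SAP does define that time separately. Harm therefore needs two steps that are not established: use of the variable, and literal coding. SAP 4.1 adds: "This study is non-comparative and no inferential statistical analyses are planned". This stands, and it limits the weight of the point.

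Third, g + 1 borrows the +1 from the formula under criticism. That is a fair caveat. It moves the size of the error by one day and leaves the direction unchanged.

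Fourth, g = 183 is only an example. Protocol 6.3.1 lets visit timing follow local practice, and the documents give no expected number of locoregional recurrences, so the total effect cannot be stated.

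Negative times are conspicuous, but nothing readable describes a check on derived times, so the plan cannot be assumed to catch them.

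**Conclusion.** The point holds: the printed formula is wrong and contradicts the sentence it is meant to specify. If coded as written, each locoregional recurrence documented g days after inclusion gets a time that is 2g days too small, assuming the SAP's +1 is intended. That makes the time zero for a recurrence on the day after inclusion and negative for any later one. Only a recurrence documented on the day of inclusion is timed correctly.

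The severity is minor. The error reaches only a secondary summary that uses this variable. The primary composite as worded, the event proportions and the incidence rates (which divide by exposure time) are not affected. Part of the appendix is not visible, so nothing is claimed about other formulas.

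**What to change.** Exchange the two dates and keep the +1: time to locoregional recurrence = date of first documented locoregional recurrence − date of inclusion + 1.

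When making the correction, confirm that any other time formulas in the full appendix, including those for censoring times, use the same order and the same +1 convention, so that event and censoring times are on one scale.

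The cost is one line of SAP wording, issued as an erratum. It needs no new data and no change of analysis method.
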